8.2.4.2 Supplementary Analysis #2

The second supplementary analysis of the primary endpoint will be performed using a treatment policy strategy (see details in [Section 8.1](#)) based on the RS. Any missing MG-ADL scores will be handled based on maximum likelihood estimation method under MAR assumption.

The same stage-wise analysis approach as primary analysis ([Section 8.2.2](#)) will be repeated.

8.2.5 Additional Analysis

An additional analysis of primary endpoint will be performed on RS under the COVID-19 hypothetical strategy (see details in [Section 8.1](#)). The same stage-wise analysis approach as primary analysis ([Section 8.2.2](#)) will be repeated.

8.2.6 Exploratory Analysis

An exploratory analysis of primary endpoint using historical MG-specific auto-antibodies as a covariate instead of Baseline MG-specific auto-antibodies. This analysis will be performed on RS under the hypothetical & treatment policy strategy (see details in [Section 8.1](#)). The same stage-wise analysis approach as primary analysis ([Section 8.2.2](#)) will be repeated.

8.3 Statistical analysis of the secondary efficacy endpoints

All secondary efficacy endpoints will be tested according to the testing strategy defined in [Section 4.6](#).

Please see below for details about the estimands attributes for the evaluation of the secondary endpoints (secondary and sensitivity analyses).

1. **Treatment Conditions:** same as described in the estimand for the primary endpoint ([Table 8-1](#)).
2. **Population:** same as described in the estimand for the primary endpoint ([Section 8.2](#)).
3. **Endpoints, ICEs and PLS:** Please see [Table 8-3](#) below.

Table 8-3: Secondary Efficacy Endpoints: Intercurrent Events and Population Level Summary by Statistical Category

Statistical Category	Endpoint	Intercurrent Event Strategy	Population Level Summary
Secondary	MG-ADL responder (≥ 2.0 points improvement from Baseline) at Day 43 (Visit 10)	The ICEs are detailed in Section 8.1 . A composite strategy will be used to handle the ICEs.	Odds ratio at Day 43 (Visit 10) analyzed using a logistic regression model adjusting for covariates for study participants receiving rozanolixizumab versus placebo, using the RS.
Secondary	Change from Baseline to Day 43 (Visit 10) in MG-C score	The ICEs are detailed in Section 8.1 . A hypothetical & treatment policy strategy will be used to handle the ICEs.	Difference in mean change from Baseline (LSMD from MMRM) to Day 43 (Visit 10) in the MG-C score for study participants receiving rozanolixizumab versus placebo.
Sensitivity	Change from Baseline to Day 43 (Visit 10) in MG-C score	The ICEs are detailed in Section 8.1 . A hypothetical & treatment policy strategy will be used to handle the ICEs.	Difference in mean change from Baseline (LSMD from CfB MMRM) to Day 43 (Visit 10) in the MG-C score for study participants receiving rozanolixizumab versus placebo, using the RS. A J2R multiple imputation approach will be utilised to assess the validity of the MAR assumption. Missing data across all treatment groups will be imputed using the placebo distribution.

Statistical Category	Endpoint	Intercurrent Event Strategy	Population Level Summary
Supplemental	Change from Baseline to Day 43 (Visit 10) in MG-C score	The ICEs are detailed in Section 8.1 . A composite strategy will be used to handle the ICEs.	
Difference in mean change from Baseline (LSMD from ANCOVA) to Day 43 (Visit 10) in the MG-C score for study participants receiving rozanolixizumab versus placebo.
 
A trimmed mean approach will be used where all missing data (including the main intercurrent events) will be imputed with the worst score of its respected questionnaire. A permutation-based test will be carried out, with the % trimming applied adaptively. The mean treatment difference of the trimmed population will be calculated on covariate-adjusted scores which are derived from an ANCOVA analysis of completers data, using the RS.

Secondary	Change from Baseline to Day 43 (Visit 10) in QMG score	Hypothetical & treatment policy strategy , same as for the MG-C secondary analysis	Difference in mean change from Baseline (LSMD from MMRM) to Day 43 (Visit 10) in the QMG score for study participants receiving rozanolixizumab versus placebo.
Sensitivity	Change from Baseline to Day 43 (Visit 10) in QMG score	Hypothetical & treatment policy strategy , same as for the MG-C sensitivity analysis	Difference in mean change from Baseline (LSMD from CfB MMRM) to Day 43 (Visit 10) in the QMG score for study participants receiving rozanolixizumab versus placebo, using the RS. A J2R multiple imputation approach will be utilised, same as the MG-C sensitivity analysis
Supplemental	Change from Baseline to Day 43 (Visit 10) in QMG score	Composite strategy , same as for the MG-C supplemental analysis	
Difference in mean change from Baseline (LSMD from ANCOVA) to Day 43 (Visit 10) in the QMG score for study participants receiving rozanolixizumab versus placebo.
 
A trimmed mean approach will be used, as the MG-C supplemental analysis

Statistical Category	Endpoint	Intercurrent Event Strategy	Population Level Summary
Secondary	Change from Baseline to Day 43 (Visit 10) in the MG Symptoms PRO 'Muscle Weakness Fatigability' score	Hypothetical & treatment policy strategy , same as for the MG-C secondary analysis	Difference in mean change from Baseline (LSMD from MMRM) to Day 43 (Visit 10) in the MG Symptoms PRO 'Muscle Weakness Fatigability' score for study participants receiving rozanolixizumab versus placebo.
Sensitivity	Change from Baseline to Day 43 (Visit 10) in MG Symptoms PRO 'Muscle Weakness Fatigability' score	Hypothetical & treatment policy strategy , same as for the MG-C sensitivity analysis	Difference in mean change from Baseline (LSMD from CfB MMRM) to Day 43 (Visit 10) in the QMG score for study participants receiving rozanolixizumab versus placebo, using the RS. A J2R multiple imputation approach will be utilised, same as the MG-C sensitivity analysis
Supplemental	Change from Baseline to Day 43 (Visit 10) in the MG Symptoms PRO 'Muscle Weakness Fatigability' score	Composite strategy , same as for the MG-C supplemental analysis	Difference in mean change from Baseline (LSMD from ANCOVA) to Day 43 (Visit 10) in the MG Symptoms PRO 'Muscle Weakness Fatigability' score for study participants receiving rozanolixizumab versus placebo. A trimmed mean approach will be used, as the MG-C supplemental analysis
Secondary	Change from Baseline to Day 43 (Visit 10) in the MG Symptoms PRO 'Physical Fatigue' score	Hypothetical & treatment policy strategy , same as for the MG-C secondary analysis	Difference in mean change from Baseline (LSMD from MMRM) to Day 43 (Visit 10) in the MG Symptoms PRO 'Physical Fatigue' score for study participants receiving rozanolixizumab versus placebo.

Statistical Category	Endpoint	Intercurrent Event Strategy	Population Level Summary
Sensitivity	Change from Baseline to Day 43 (Visit 10) in the MG Symptoms PRO 'Physical Fatigue' score	Hypothetical & treatment policy strategy , same as for the MG-C sensitivity analysis	Difference in mean change from Baseline (LSMD from CfB MMRM) to Day 43 (Visit 10) in the MG Symptoms PRO 'Physical Fatigue' score for study participants receiving rozanolixizumab versus placebo, using the RS. A J2R multiple imputation approach will be utilised, same as the MG-C sensitivity analysis
Supplemental	Change from Baseline to Day 43 (Visit 10) in the MG Symptoms PRO 'Physical Fatigue' score	Composite strategy , same as for the MG-C supplemental analysis	Difference in mean change from Baseline (LSMD from ANCOVA) to Day 43 (Visit 10) in the MG Symptoms PRO 'Physical Fatigue' score for study participants receiving rozanolixizumab versus placebo. A trimmed mean approach will be used, as the MG-C supplemental analysis
Secondary	Change from Baseline to Day 43 (Visit 10) in the MG Symptoms PRO 'Bulbar Symptoms' score	Hypothetical & treatment policy strategy , same as for the MG-C secondary analysis	Difference in mean change from Baseline (LSMD from MMRM) to Day 43 (Visit 10) in the MG Symptoms PRO 'Bulbar Symptoms' score for study participants receiving rozanolixizumab versus placebo.
Sensitivity	Change from Baseline to Day 43 (Visit 10) in the MG Symptoms PRO 'Bulbar Symptoms' score	Hypothetical & treatment policy strategy , same as for the MG-C sensitivity analysis	Difference in mean change from Baseline (LSMD from CfB MMRM) to Day 43 (Visit 10) in the MG Symptoms PRO 'Bulbar Symptoms' score for study participants receiving rozanolixizumab versus placebo, using the RS. A J2R multiple imputation approach will be utilised, same as the MG-C sensitivity analysis

Statistical Category	Endpoint	Intercurrent Event Strategy	Population Level Summary
Supplemental	Change from Baseline to Day 43 (Visit 10) in the MG Symptoms PRO 'Bulbar Symptoms' score	Composite strategy , same as for the MG-C supplemental analysis	Difference in mean change from Baseline (LSMD from ANCOVA) to Day 43 (Visit 10) in the MG Symptoms PRO 'Bulbar Symptoms' score for study participants receiving rozanolixizumab versus placebo. A trimmed mean approach will be used, as the MG-C supplemental analysis

Note: CfB=Change from Baseline; LSMD=Least Squares Mean Difference; MMRM=mixed model for repeated measures; ANCOVA= analysis of covariance; MAR=Missing at Random

8.3.1 MG-ADL Responder Rate at Visit 10 (Day 43)

See [Section 8.2.1](#) for the derivation of MG-ADL total score.

Study participants will be classified as responders at Visit 10 if the value is at least a 2-point improvement (decrease) from Baseline at Visit 10 (Day 43).

Analysis will be based on the RS under the composite strategy (see details in [Section 8.1](#)). Any missing data scores (including missing data due to the intercurrent events) will also be imputed as non-responders. Note that this endpoint is not part of the formal secondary endpoint testing strategy.

The number and percentage of study participants who are MG-ADL responders at Day 43 will be presented by treatment group and RLZ total for each stage. The odds ratio of the responder rates at Day 43 will be estimated and tested between treatment groups (each rozanolixizumab dose vs placebo) for each stage separately using logistic regression model with factors of treatment group, Baseline MG-ADL score and stratification factors (MuSK+/- and AChR+/-). The odds ratio with associated 95% CI and p-value based on the Wald test will be presented. Region may be added as an additional factor in the logistic regression model if significant in the primary analysis.

The odds ratios, 95% CIs, and p-values from each stage will be combined using the same inverse normal method used in the primary efficacy endpoint.

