4 STATISTICAL/ANALYTICAL ISSUES

4.1 Adjustments for covariates

The efficacy analyses will be adjusted for the following covariates:

- Baseline MG-ADL score,
- Region (North America, Europe, and Asia [excluding Japan], Japan),
- Stratification factors – MG-specific autoantibodies, including muscle specific kinase [MuSK(+/-)] and acetylcholine receptor [AChR(+/-)], both as binary variables.

In statistical modeling, the stratification factors MuSK(+/-) and AChR(+/-) will be based on the values from MG-specific autoantibody assessment at Baseline. In case Baseline MG-specific autoantibody result is missing (and not resolved after data queries), a post-Baseline measurement may be used. If this is not available, then the historical result will be used in the model; if the historical result is missing as well, the stratification factor from IWRS randomization file will be used to determine values used in the model (i.e., if the stratification is MuSK in IWRS, then

MuSK(+/-) will be imputed as positive, otherwise negative; similarly, if stratification factor is AChR in IWRS, then AChR(+/-) will be imputed as positive, otherwise negative).

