8.2.2 Primary analysis of the primary efficacy endpoint

The primary analysis is based on the RS under the hypothetical & treatment policy strategy (see details in [Section 8.1](#)). Any missing MG-ADL scores (including missing data after the intercurrent events) will be handled based on maximum likelihood estimation method under MAR assumption.

A stage-wise MMRM with treatment group, Baseline MG-ADL score, region, stratification factor(s) including MuSK(+/-) and /or AChR(+/-), and treatment group by day (interaction term) as fixed factors and study participant as a random effect. The MMRM will include Days 8, 15, 22, 29, 36 and 43.

The model will utilize an unstructured covariance pattern for the repeated measures. If the model does not converge using the unstructured pattern, then an autoregressive covariance structure

will be used. The Kenward-Roger approximation will be used to estimate the denominator degrees of freedom.

For each stage, the least squares means (LSMs) of each treatment group, and the least squares mean differences (LSMDs) between each dose group and placebo will be reported for Day 43 (Visit 10), along with the corresponding 2-sided 97.5% CIs and p-values.

The study follows a 2-stage group sequential adaptive design using combination test (Lehmacher and Wassmer, 1999) based on the inverse-normal method of combining independent stagewise p-values (Hedges and Olkin, 1985)

The analysis takes into account that the study is a 2-stage group sequential adaptive design assuming equal weighting of each stage, with weights = $1/\sqrt{2}$:

- Stage 1 – Cohort up to the formal IA
- Stage 2 – Cohort post-IA

The following sequential test statistic will be used to test the global null hypothesis at the end of stage 2:

$$T = \sum_{i=1}^2 w_i \phi^{-1}(1 - p_i)$$

Where subscript $i = 1, 2$ represents the stage, p_i represents the appropriate multiplicity adjusted p-value at stage i (for example at stage 1, $p_1 = \min(2 * p_{\min}, 1)$ where p_{\min} is the minimum of the two nominal p-values), the weights $w_{ki} = 1/\sqrt{2}$ satisfy $\sum_{i=1}^2 w_{ki}^2 = 1$ and ϕ^{-1} is the inverse cumulative standard normal distribution function. The test statistic T and $z = \phi^{-1}(1 - p_i)$ have a standard normal distribution, (Lehmacher and Wassmer, 1999).

The combined p-value (2-sided) for the 2 stages, which tests the global null hypothesis, can be calculated by:

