8.4.3 Time to MG-ADL response (≥ 2.0 points improvement from Baseline)

Time to MG-ADL response (in days) is defined as Date of First MG-ADL Response— Date of MG-ADL Baseline + 1.

Study participants who use rescue therapy prior to Day 43 or who are withdrawn from the treatment/study due to TEAEs before achieving first MG-ADL response will be censored at time of event. Study participants who never achieve a response by Day 43 will be censored at the date of their last MG-ADL assessment.

The number of study participants with 8, 12, 24, 32, 43 days to first MG-ADL response and number of censored study participants will be summarized descriptively.

Time to first MG-ADL response will be analyzed using a Cox Proportional Hazards model including fixed terms for treatment and stratification factors (MuSK+/- or AChR+/-). This model will be performed separately for study participants included in the interim analysis and for all study participants overall. Region may be added as an additional factor in the Cox Proportional Hazards model if it is significant in the primary analysis.

The Hazard Ratio (test/reference), 95% CI and p-values for each treatment comparison of interest will be presented for the Stage 1 (interim analysis), Stage 2 and overall (all data combined).

The log-hazard ratio, standard error estimates and (1-sided) p-values from the separate stage-wise Cox Proportional Hazards models for the relevant treatment group will be used to create overall p-values and repeated confidence intervals using the same methodology as the primary efficacy analysis.

The time to first MG-ADL response will be presented graphically using a Kaplan-Meier curve by treatment group, RLZ total. See details in [Section 9.3.2](#).

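### SAP 8.3.1 and 8.4.3 leave the region term in the logistic and Cox models to discretion after a significance test on the trial data, in conflict with SAP 4.1

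*SAP*

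**What the plan says.** SAP 4.1 opens with "The efficacy analyses will be adjusted for the following covariates" and lists Baseline MG-ADL score, region in four categories, and the two antibody factors. No condition is attached.

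SAP 8.3.1 gives the responder logistic model treatment group, Baseline MG-ADL and the antibody factors, and then adds: "Region may be added as an additional factor in the logistic regression model if significant in the primary analysis". SAP 8.4.3 gives the Cox model treatment and the antibody factors only, followed by: "Region may be added as an additional factor in the Cox Proportional Hazards model if it is significant in the primary analysis".

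The primary analysis that is to supply the region test is described in SAP 8.2.2 as "A stage-wise MMRM with treatment group, Baseline MG-ADL score, region" and further terms, fitted to Stage 1 and Stage 2 separately. For the responder endpoint, the odds ratios, confidence intervals and "p-values from each stage will be combined using the same inverse normal method used in the primary efficacy endpoint". SAP 8.4.3 combines its stage-wise log-hazard ratios in the same way.

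Protocol 9.4.2 specifies both models without region and without any conditional rule. SAP 3.9, which lists the changes from the protocol, does not mention the rule.

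**The concern.** There are three difficulties.

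First, the two model sections contradict the general covariate section, so the SAP gives two answers to whether region is in these models.

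Second, the choice is made after outcome and treatment data have been analysed together. It is also permissive: region could be left out even when its test is significant. Two analysts following the text could report different odds ratios from the same data.

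Third, the trigger has no single referent. Each stage has its own MMRM and therefore its own region test, and the SAP does not say which one governs or whether one decision binds both stages. If each stage followed its own test, one stage could be adjusted for region and the other not. Odds and hazard ratios change meaning with the covariates conditioned on, so the combined estimate could then mix two different quantities.

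**Working it through.** The plan gives no figure on this point, so there is none to reproduce. The check is a comparison of the texts, followed by arithmetic and a simulation to gauge size.

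**Step 1. Covariates side by side.**

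| Source | Region | Baseline MG-ADL |
|---|---|---|
| SAP 4.1, efficacy analyses | Yes, unconditional | Yes |
| SAP 8.2.2, MMRM | Yes | Yes |
| SAP 8.2.4.1, trimmed-mean ANCOVA | Yes | Yes |
| SAP 8.3.1, logistic | Optional, after a test | Yes |
| Protocol 9.4.2, logistic | No | Yes |
| SAP 8.4.3, Cox | Optional, after a test | No |
| Protocol 9.4.2, Cox | No | No |

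On region, the logistic and Cox models are the exceptions to 4.1. The Cox model also departs from 4.1 on Baseline MG-ADL.

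**Step 2. Can the trigger be evaluated?** The level can be inferred: SAP 3.1 sets a two-sided 0.05 default. The stage cannot. SAP 8.2.2 combines the treatment comparisons across stages, and no combined region test is defined. SAP 8.4.3 also asks for an overall Cox fit, for which no pooled MMRM exists to supply a region test.

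**Step 3. How often would the stages disagree?** With no region effect and independent stages, the chance that exactly one test is significant at level a is 2a(1 − a).
- a = 0.05: 2 × 0.05 × 0.95 = 0.095, or 9.5%.
- a = 0.10: 2 × 0.10 × 0.90 = 0.18, or 18%.

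**Step 4. How far can conditioning move an odds ratio?** Assume two equal groups with control odds 0.58 and 1.73 (a covariate odds ratio of about 3) and a conditional treatment odds ratio of 3.
- Control response: 0.58/1.58 = 0.367 and 1.73/2.73 = 0.634; mean 0.500.
- Treated odds are 1.74 and 5.19. Response: 1.74/2.74 = 0.635 and 5.19/6.19 = 0.838; mean 0.737.
- Unadjusted odds ratio: (0.737/0.263)/(0.500/0.500), about 2.8 against 3.0.

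**Step 5. Simulation.** There were 2,000 runs per scenario, with 30 per arm in each stage and SD 3.5 (both from SAP 2.4). A Day 43 ANCOVA stood in for the MMRM, with a 3-df region test at 0.05. A logistic model was then fitted per stage and the Wald statistics were combined with weights 1/√2. The following are assumptions not in the documents: a region mix of 50/30/10/10%, 10% MuSK-positive, the baseline distribution, and region effects of zero, moderate (0, 1, 2, −1 points) or strong (0, 2, 3, −2 points).

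| Region effect | Exactly one stage significant | Type I error: always include / stage-wise rule | Power at 2 points: always include / stage-wise rule | Median Stage 1 odds ratio at 2 points: without / with region |
|---|---|---|---|---|
| None | about 10% | 0.043 / 0.043 | 0.681 / 0.675 | 2.59 / 2.71 |
| Moderate | 47–48% | 0.052 / 0.052 | 0.667 / 0.668 | 2.53 / 2.70 |
| Strong | 21–22% | 0.058 / 0.058 | 0.645 / 0.641 | 2.47 / 2.73 |

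The Monte Carlo standard error of a 5% rate is √(0.05 × 0.95/2000), about 0.005. The odds-ratio gap of 0.12 with no region effect reflects small-sample inflation. Its growth to 0.17 and 0.26 reflects non-collapsibility.

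**The case against.** The strongest reply is that little depends on this. SAP 8.3.1 places the responder endpoint outside the formal secondary testing strategy, and it appears in none of the families in SAP 4.6. Time to response is among the other efficacy endpoints. SAP 8.3 does say that all secondary endpoints are tested under 4.6, which is awkward, but 8.3.1 is the more specific text. The inverse normal test also does not need the same covariates in both stages to be valid under the null, and the selection is on region, not on treatment. All of this stands.

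There is also a plausible reason to leave region out. Stage 1 has about 30 per arm, region has four levels, and SAP 3.7 shows that Asia excluding Japan is Taiwan alone. Sparse cells are a real risk in a logistic model. That supports a simpler model, but not a model chosen after the results are known.

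A reader might infer more than the documents support:
- **That the SAP prescribes different covariates by stage.** It does not. A single decision applied to both stages fits the wording equally well.
- **That region enters if and only if it is significant.** The wording is permissive, not a fixed rule.
- **That no significance level exists.** SAP 3.1 supplies a default; only the deciding stage is missing.
- **That always including region is the only sound repair.** The base models agree with Protocol 9.4.2 on region, so keeping them and amending 4.1 is equally defensible.

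**Conclusion.** The point holds as a matter of pre-specification and reproducibility. The optional region term contradicts SAP 4.1, has no basis in Protocol 9.4.2, is not declared in SAP 3.9, and cannot be applied uniquely because the primary analysis produces one region test per stage.

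The consequence is modest. No primary or hierarchical test is affected, and simulated type I error was the same under the stage-wise rule and under fixed inclusion (0.043 to 0.058 for both). What is at risk is the meaning of the reported odds and hazard ratios. The 9.5% figure assumes a stage-by-stage decision, a 0.05 level and no region effect. The larger disagreement rates, and the shift from 3.0 to 2.8, rest on assumed covariate effects that the documents do not give.

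**What to change.** Delete the two sentences that make region optional (SAP 8.3.1 and 8.4.3). Before unblinding, fix one covariate set for each model, identical in Stage 1, Stage 2 and any overall fit. There are two acceptable routes:

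1. **Include region** in both models, as 4.1 states, with a pre-specified rule for pooling sparse regions. Protocol 9.4.2 has no region term, so list this in SAP 3.9.
2. **Keep the protocol's models without region** and state in 4.1 that these two models are exempt.

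At the same time, reconcile the Cox model's omission of Baseline MG-ADL with 4.1, either by exempting it or by adding the term. Adding it would be a change from Protocol 9.4.2 and belongs in SAP 3.9.

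The cost is SAP wording only. The small downside of the first route is the need for a pooling rule, which may cut across the SAP's separation of Japan from the rest of Asia.
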